6.13. Bioanalytical and Pharmacokinetic/Pharmacodynamic Methods

Pharmacokinetic (PK), pharmacodynamic (PD), and biomarker analyses will not be conducted.

6.14. Safety Analyses

Detailed analyses and discussion of Study JAHN safety data are more thoroughly assessed in the context of combining the safety data from the originating Studies, JAHL, JAHM, and JAIY with the safety data from Study JAHN. The planned analyses are described in the compound level safety standards.

For the purpose of Study JAHN alone, the following are planned to be analyzed:

- duration of exposure by Treatment Periods 1 and 2
- overview of AEs by Treatment Periods 1 and 2
- treatment-emergent adverse events (TEAEs) by PT nested within System Organ Class (SOC) by Treatment Periods 1 and 2
- serious adverse events (SAEs) by PT nested within SOC by Treatment Periods 1 and 2, and listing of SAEs in Treatment Periods 1 and 2 combined (one listing)
- AEs leading to permanent study drug discontinuation by PT nested within SOC for Treatment Period 1, and listing of AEs leading to permanent study drug discontinuation and discontinuation from the study in Treatment Periods 1 and 2 combined (one listing)
- listing of deaths in Treatment Periods 1 and 2 combined (1 listing), if any
- clinical laboratory evaluation and vital signs in terms of box plots, descriptive and treatment-emergent summaries in Treatment Period 1
- clinical laboratory and vital signs in terms of box plots and descriptive summaries in Treatment Periods 1 and 2 combined

The general methods used to summarize safety data, including the definition of baseline value, are described in Section 6.2.

Safety analyses will be conducted according to the safety population defined in Section 6.2.1 and the treatment groups defined in Table JAHN.6.1 in Section 6.2.1.

Unless otherwise specified, by-visit summaries will include planned on-treatment visits. For tables that summarize events (such as AEs), on-treatment and follow-up data will be included up to 30 days after the last dose of treatment or up to dose or treatment change, where applicable.

For the February 2021 DBL and Final DBL summary and analyses, safety analyses will be done for the disposition summary and the below AE tables summarized in Period 1 and Period 2, respectively. Other detailed safety assessments will be implemented in the integrated safety analysis plan with other studies (I4V-MC-JAIN, I4V-MC-JAIW, and I4V-MC-JAIX).

- overview of AEs
- TEAEs
- AEs leading to permanent discontinuation of study drug
- SAEs

6.14.1. Extent of Exposure

Duration of exposure (in days) for Treatment Periods 1 and 2 will be calculated as follows:

- duration of exposure to IP in Treatment Period 1: minimum (date of last dose of study drug, Week 52 date) – date of first dose of study drug in Study JAHN + 1.
- duration of exposure to IP in Treatment Period 2: minimum (date of last dose of study drug [$>$ Week 52 date], $>$ Week 52 date) – date of first dose of study drug in Study JAHN in Treatment Period 2 + 1

Last dose of study drug is calculated as last date on study drug or censored at dose or treatment change according to the treatment groups defined in Section 6.2.1. For patients discontinuing treatment and the treatment stop date is missing, the duration of exposure will use date of last visit in exposure calculation. For patients whose treatment discontinuation is unknown because they were lost to follow-up, the date of the visit (scheduled or unscheduled) just prior to the last visit (if the treatment stop date is missing) is used for this calculation.

Descriptive statistics will be provided for patient-days of exposure. Total patient-years of exposure (PYE) will be reported for each treatment group by Treatment Periods 1 and 2 for duration of exposure.

Exposure ranges for Treatment Period 1 will be summarized as follows:

- >0 weeks, ≥ 4 weeks, ≥ 8 weeks, ≥ 12 weeks, ≥ 16 weeks, ≥ 24 weeks, ≥ 32 weeks and ≥ 52 weeks
- >0 to <4 weeks, ≥ 4 weeks to <8 weeks, ≥ 8 weeks to <12 weeks, ≥ 12 weeks to <16 weeks, ≥ 16 weeks to <24 weeks, ≥ 24 weeks to <32 weeks, ≥ 32 weeks to <52 weeks, and ≥ 52 weeks

Exposure ranges for Treatment Period 2 will be summarized as follows:

- >52 weeks, ≥ 56 weeks, ≥ 60 weeks, ≥ 64 weeks, ≥ 68 weeks, ≥ 76 weeks, ≥ 84 weeks, ≥ 92 weeks, ≥ 104 weeks, ≥ 120 weeks, ≥ 136 weeks, ≥ 152 weeks, ≥ 168 weeks, ≥ 184 weeks, and ≥ 200 weeks
- ≥ 52 to <56 weeks, ≥ 56 weeks to <60 weeks, ≥ 60 weeks to <64 weeks, ≥ 64 weeks to <68 weeks, ≥ 68 weeks to <76 weeks, ≥ 76 weeks to <84 weeks, ≥ 84 weeks to <92 weeks, ≥ 92 weeks to <104 weeks, ≥ 104 weeks to <120 weeks, ≥ 120 weeks to <136 weeks, ≥ 136 weeks to <152 weeks, ≥ 152 weeks to <168 weeks, ≥ 168 weeks to <184 weeks, ≥ 184 weeks to <200 weeks, and ≥ 200 weeks

Overall exposure by Treatment Periods 1 and 2 will be summarized in total PYE, which is calculated according to the following formula:

$PYE = \text{sum of duration of exposure in days (for all patients in treatment group)} / 365.25.$

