- **Screening and baseline period:** Screening should occur during the last visit of the originating study unless the patient received oral systemic AD treatment as rescue therapy during the originating study and needs additional time to complete the required 4-week washout period or the sponsor gave approval.
- **Treatment Period 1:** Treatment period from Week 0 to Week 52. Patients will be classified as responders, partial responders or nonresponders at the entry of Study JAHN based on the criteria given in Section 5.1.

- Treatment Period 2: Treatment period from Week 52 to 200 and will contain a randomized withdrawal and downtitration substudy. At Week 52, all patients will be evaluated for substudy eligibility, and the criteria are given in the Protocol. Patients not entered in the substudy will continue on their current treatment.
- Posttreatment follow-up period: Period from Week 200 (Visit 22) or Early Termination Visit (ETV) to approximately 28 days after the last dose of IP.

Abbreviations: BARI = baricitinib; IGA = Investigator’s Global Assessment; TCS = topical corticosteroids.

a Background TCS may be initiated or reinitiated at any time during the study, following the guidelines in the Protocol (Section 7.7.1) and will be provided as part of rescue or retreatment any time a patient’s IGA score becomes ≥ 3 as described in the Protocol (Sections 5.1.2.1 and 5.1.3.1).

b Eligible patients will be rerandomized in the withdrawal and downtitration substudy as described in the Protocol (Section 5.1.3.1). Patients who do not enroll in the substudy will remain on their treatment.

c Patients enrolled in the substudy will automatically be retreated if their IGA score becomes ≥ 3 as described in the Protocol (Section 5.1.3.1).

d Rescue is available as described in the Protocol (Section 5.1.2.1).

Figure JAHN.5.1. Illustration of study design for Clinical Protocol I4V-MC-JAHN.

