BARI 2 mg	BARI 2 mg followed to end of Treatment Period 1 or censored at dose or treatment change
PBO/BARI 1 mg/BARI 2 mg to BARI 4 mg	PBO/BARI 1 mg/BARI 2 mg switching to BARI 4 mg at entry to Study JAHN followed to end of Treatment Period 1 or censored at dose or treatment change
BARI 4 mg	BARI 4 mg followed to end of Treatment Period 1 or censored at dose or treatment change
Pooled BARI	BARI 1 mg/BARI 2 mg/BARI 4 mg at entry to Study JAHN followed to end of Treatment Period 1 or censored at dose or treatment change
Treatment Groups for Treatment Period 2 (Week 52-200)	Definition
BARI 2 mg to PBO	Randomized to PBO in Treatment Period 2 (previously treated with BARI 2 mg) followed to end of study or censored at retreatment with BARI 2 mg

Treatment Groups for Treatment Period 2 (Week 52-200)	Definition
BARI 2 mg to BARI 1 mg	Randomized to BARI 1 mg in Treatment Period 2 (previously treated with BARI 2 mg) followed to end of study or censored at retreatment with BARI 2 mg
BARI 2 mg to BARI 2 mg	Randomized to stay on BARI 2 mg in Treatment Period 2 followed to end of study
BARI 4 mg to PBO	Randomized to PBO in Treatment Period 2 (previously treated with BARI 4 mg) followed to end of study or censored at retreatment with BARI 4 mg
BARI 4 mg to BARI 2 mg	Randomized to BARI 2 mg in Treatment Period 2 (previously treated with BARI 4 mg) followed to end of study or censored at retreatment with BARI 4 mg
BARI 4 mg to BARI 4 mg	Randomized to stay on BARI 4 mg in Treatment Period 2 followed to end of study
BARI 2 mg	Not part of the substudy, stayed on BARI 2 mg in Treatment Period 2 followed to end of study (this treatment group includes the open-label BARI 2 mg addendum patients)
BARI 4 mg	Not part of substudy, stayed on BARI 4 mg in Treatment Period 2 followed to end of study
Treatment Group for Treatment Periods 1 and 2 (Week 0-104) (for Box Plots Only)	Definition
PBO	Placebo at entry to Study JAHN followed to end of study or censored at treatment change
BARI 1 mg	BARI 1 mg followed to end of study or censored at dose or treatment change
BARI 2 mg to PBO	BARI 2 mg in Treatment Period 1, rerandomized to PBO in Treatment Period 2 followed to end of study or censored at retreatment with BARI 2 mg
BARI 2 mg to BARI 1 mg	BARI 2-mg in Treatment Period 1, rerandomized to BARI 1 mg in Treatment Period 2 followed to end of study or censored at retreatment with BARI 2 mg

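### Two SAP derivation rules are wrong as printed: Period 2 exposure is timed from the first Period 2 dose but binned on study weeks 52 to 200, and change in presenteeism subtracts baseline absenteeism

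*SAP*

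**What the plan says.** **Period 2 exposure.** Under SAP Section 6.14.1, Period 2 duration is the earlier of two dates minus "date of first dose of study drug in Study JAHN in Treatment Period 2 + 1". The first date is that of the last dose. The second is printed only as an unspecified date later than Week 52. A separate sentence ends exposure for each treatment group: "Last dose of study drug is calculated as last date on study drug or censored at dose or treatment change".

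The section then gives two lists of ranges. The Period 1 list ("Exposure ranges for Treatment Period 1 will be summarized as follows") starts above 0 weeks and ends at 52 weeks or more. The Period 2 list ("Exposure ranges for Treatment Period 2 will be summarized as follows") starts above 52 weeks and ends at 200 weeks or more, with 15 mutually exclusive intervals. Section 5.1 defines Period 2 as "Treatment period from Week 52 to 200 and will contain a randomized withdrawal and downtitration substudy". In Table JAHN.6.1, patients re-randomised from 2 mg to placebo or 1 mg are "followed to end of study or censored at retreatment with BARI 2 mg", and the 4 mg groups have a parallel rule.

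**Presenteeism.** In the WPAI-AD rows of Table JAHN.6.6, the change score for presenteeism is the observed presenteeism value minus the baseline absenteeism value. The change rows for absenteeism, overall work impairment and activity impairment each subtract their own baseline. So does the general change-from-baseline rule in Section 6.2.4.

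**The concern.** The Period 2 duration and the Period 2 ranges have different time origins. One starts at the first Period 2 dose; the other matches the visit calendar counted from entry into JAHN. In Period 1 the two origins coincide, so the problem appears only in Period 2.

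The groups most exposed are those re-randomised to placebo or a lower dose. They are censored at retreatment, so short durations are possible there, and short durations are what the printed ranges cannot hold. How many such patients there are is not in the documents. The table also matters to the addendum: its stated purpose (Protocol Section 3) is to enlarge the long-term 2 mg exposure database, Appendix 1 sends its exposure analysis to Section 6.14.1, and addendum patients outside the substudy are in the Period 2 2 mg group.

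The presenteeism row, if programmed as printed, reports a difference between two different scores under the label of a change score. Section 6.12 and Appendix 1 (APP.1.2.13) both name Table JAHN.6.6 as the source of derivations. The row therefore feeds the nonresponder MMRM and the responder and open-label summaries.

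**Working it through.** **Exposure**

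Inputs: Period 2 is Weeks 52 to 200 (Section 5.1, Table JAHN.6.1). Duration is last dose − first Period 2 dose + 1 (Section 6.14.1). The first Period 2 dose is taken on the Week 52 date.

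Formula: days = (study week of last dose − 52) × 7 + 1; weeks = days / 7.

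| Study week of last dose | Days | Weeks | Printed interval for this duration | Interval on the study-week scale |
|---|---|---|---|---|
| 56 | 29 | 4.1 | none | 56 to <60 |
| 60 | 57 | 8.1 | none | 60 to <64 |
| 64 | 85 | 12.1 | none | 64 to <68 |
| 68 | 113 | 16.1 | none | 68 to <76 |
| 76 | 169 | 24.1 | none | 76 to <84 |
| 84 | 225 | 32.1 | none | 84 to <92 |
| 92 | 281 | 40.1 | none | 92 to <104 |
| 104 | 365 | 52.1 | 52 to <56 | 104 to <120 |
| 120 | 477 | 68.1 | 68 to <76 | 120 to <136 |
| 136 | 589 | 84.1 | 84 to <92 | 136 to <152 |
| 152 | 701 | 100.1 | 92 to <104 | 152 to <168 |
| 168 | 813 | 116.1 | 104 to <120 | 168 to <184 |
| 184 | 925 | 132.1 | 120 to <136 | 184 to <200 |
| 200 | 1037 | 148.1 | 136 to <152 | ≥200 |

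Seven of the 14 visit weeks give no interval, and the two right-hand columns agree at none of the 14. Starting Period 2 dosing the day after Week 52 removes one day and changes no row.

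Upper limit: with Week 52 four days early and Week 200 four days late, 148 × 7 + 4 + 4 + 1 = 1045 days = 149.3 weeks. The 152-week edge needs 152 × 7 = 1064 days, so on this basis the top four of the 15 intervals cannot be reached. The ±4 days at Week 200 is an assumption, because the supplied visit schedule ends at Week 104 plus follow-up.

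**Presenteeism**

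Write P for presenteeism, (Q5 / 10) × 100, and A for absenteeism, (Q2 / [Q2 + Q4]) × 100.

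Error per patient = (observed P − baseline A) − (observed P − baseline P) = baseline P − baseline A.

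The algebraic range is −100 to +100 points. Baseline values are not in the documents, so the following are assumed illustrations:

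- Baseline A 10, P unchanged at 40: printed rule 40 − 10 = +30; correct value 0.
- Baseline A 60, P unchanged at 30: printed rule 30 − 60 = −30; correct value 0.
- Baseline A 0, P improving from 60 to 20: printed rule 20 − 0 = +20; correct value 20 − 60 = −40. The sign reverses.

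**The case against.** **The ranges were probably meant as study weeks.** The diary-window table in Section 6.2.2 counts Period 2 days from that period's start but names the weeks by study week (Week 53 is days 1 to 7). The Period 1 and Period 2 exposure lists also join into one scale, 0 to 52 and then 52 to 200. On that reading a label is missing, and a simple check of counts would reveal the unclassified patients. This is a fair account of intent. But the diary table does not govern exposure, and nothing in Section 6.14.1 says the ranges are anything other than ranges of Period 2 exposure. The text has to change on either reading.

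**Four unreachable intervals is not strictly proven.** When a treatment stop date is missing, the section uses the last visit, which could be the follow-up visit about 28 days after the last dose. Then 1037 + 28 = 1065 days = 152.1 weeks, just over the 152-week edge. This stands as a rare exception for the lowest of the four intervals only.

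**The exposure table may not be produced.** Section 6.14 lists "duration of exposure by Treatment Periods 1 and 2" for JAHN alone, but for the February 2021 and final locks it names only disposition and four adverse-event tables. This stands and limits the consequence.

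**The presenteeism error is an evident copying slip in an exploratory measure.** In the randomised 2 mg versus 4 mg nonresponder comparisons it shifts the group means without systematically biasing the difference. That is right. The mean changes themselves would still be wrong, as would the responder and open-label summaries, where there is no such contrast. The −100 extreme would need absenteeism of 100%, at which a score for impairment while working means little.

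**Conclusion.** Both errors hold. Taken literally, the Period 2 exposure table would omit every patient whose Period 2 exposure ends before 52 weeks and misplace those who remain at every scheduled visit week. The presenteeism change would be off by the gap between the two baseline scores and can reverse direction.

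The reach is limited. Patient-days and total patient-years come from days and do not use the ranges. WPAI-AD is exploratory. No primary or secondary endpoint is touched. The corrections should be made, but they do not threaten the trial's conclusions. The exposure figures rest on nominal visit timing and the stated window assumption; the presenteeism examples are illustrative.

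One related query, not counted as an error: the rebound rule in Table JAHN.6.4 requires a percent change in EASI of at least 125, that is, a score of at least 2.25 times baseline. With EASI capped at 72, no patient with baseline above 72 / 2.25 = 32 can meet it, and rebound has no row in the current Table JAHN.6.5.

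**What to change.** 1. In Section 6.14.1, keep the Period 2 clock and make the second argument of the minimum the end-of-Period-2 (Week 200) date.
2. Subtract 52 from each Period 2 edge: >0, then ≥4, 8, 12, 16, 24, 32, 40, 52, 68, 84, 100, 116, 132 and 148 weeks, with matching intervals. A last dose at Week 68 (16.1 weeks) then falls in 16 to <24, and one at Week 200 (148.1 weeks) in the top range. Do not instead count from the first JAHN dose: that would credit about 52 weeks of Period 1 treatment to Period 2 groups, including those re-randomised to placebo. Relabelling the existing ranges as study week of last dose would classify everyone, but it would no longer summarise the duration that the section defines.
3. State whether the Period 2 exposure table is still to be produced, given the shorter list for the final lock.
4. In Table JAHN.6.6, subtract baseline presenteeism in the presenteeism change row.
5. Ask the sponsor to confirm what the 125 in the rebound row refers to, or to delete the row.

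The cost is one formula argument, one list of edges and one word, in the SAP and the dataset specifications. In addition, the presenteeism and Period 2 exposure programs behind existing outputs need a check, because data to Week 104 were locked before Version 8 (Section 3).

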6.14.2. Adverse Events

Adverse events are recorded in the eCRFs. Each AE will be coded to SOC and PT using the MedDRA version that is current at the time of DBL. Severity of AEs is recorded as mild, moderate, or severe. TEAEs will be analyzed by Treatment Periods 1 and 2.

A TEAE is defined as an event that first occurred or worsened in severity after the first dose of study treatment in Study JAHN and on or prior to the last visit date during the analysis period. The analysis period is defined as the treatment period plus up to 30 days off-drug follow-up time.

Adverse events are classified based upon the MedDRA PT. The MedDRA Lowest Level Term (LLT) will be used in defining which events are treatment emergent. The maximum severity for each LLT during the baseline period up to first dose of the study medication in Study JAHN will be used as baseline. If an event with missing severity is preexisting during the baseline period, and persists during the treatment period, then the baseline severity will be considered mild for determining treatment emergence (ie, the event is treatment emergent if the severity is coded moderate or severe postbaseline and not treatment emergent if the severity is coded mild postbaseline). If an event occurring postbaseline has a missing severity rating, then the event is considered treatment emergent unless the baseline rating is severe, in which case the event is not treatment emergent. The day and time for events where onset is on the day of the first dose of study treatment will both be used to distinguish between pretreatment and posttreatment in order to derive treatment-emergence. Should there be insufficient data for AE start date to make this comparison (eg, the AE start year is the same as the treatment start year, but the AE start month and day are missing), the AE will be considered treatment emergent.

In general, summaries will include the number of patients in the safety population (N), frequency of patients experiencing the event (n), and relative frequency (ie, percentage; $n/N*100$). For any events that are gender specific based on the displayed PT, the denominator used to compute the percentage will only include patients from the given gender.

In an overview table, the number and percentage of patients in the safety population who experienced death, an SAE, any TEAE, discontinuation from the study due to an AE, permanent discontinuation from study drug due to an AE, or a severe TEAE will be summarized by treatment group.

The number and percentage of patients with TEAEs will be summarized by treatment group for both Treatment Periods 1 and 2 by MedDRA PT nested within SOC with decreasing frequency in SOC, and events ordered within each SOC by decreasing frequency in the baricitinib 4-mg group.

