For patients who do not require washout, baseline will be the last visit of the originating study. Patients who received oral systemic AD treatment as rescue therapy during the originating study require a 4-week washout and will have an additional screening visit in Study JAHN (Visit 1 [Week 0]). The assessments collected at this visit will provide the Study JAHN baseline for these patients. If labs were not collected at this visit, then the most recent lab value collected at the last visit of the originating study will be used as baseline.

Period 2

For analysis of endpoints assessed at scheduled visits in Period 2, baseline from originating study will be used for categorical endpoints, such as EASI75, Itch NRS ≥ 4 -point improvement response, etc. Baseline from originating study will also be used for EASI-related, continuous endpoints, such as EASI change or percent change from baseline. For the other continuous endpoints such as Itch NRS and DLQI change from baseline, the analysis will be done using the Week 52 baseline. The methodology for defining Week 52 as the baseline is the same as the methodology for defining Week 0 of the originating study described above, anchoring on the first study drug administration of Period 2.

Safety Analyses

Safety analyses for treatment Period 1, and for Treatment Periods 1 and 2 combined (box plots of laboratory analytes and vital signs) will be conducted using the Study JAHN baseline, which is defined as the last nonmissing scheduled (planned) measurement on or prior to the date of first study drug administration for continuous measures by-visit analyses and non-missing measurements on or prior to the date of first study drug administration in Study JAHN for all other analyses. Safety analyses for Treatment Period 2 will be conducted for AEs only. Baseline for Treatment Period 2 is defined as nonmissing measurements on or prior to the date of first study drug administration in Treatment Period 2 of Study JAHN.

Postbaseline

Period 1(Weeks 0 to 52)

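### SAP 6.14.2 anchors Period 2 TEAEs to the first JAHN dose, in conflict with the Period 2 AE baseline in 6.2.2; read literally, it credits persisting Period 1 events to Period 2 arms

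*SAP*

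**What the plan says.** Section 6.14.2 of the SAP states that "TEAEs will be analyzed by Treatment Periods 1 and 2". It then defines treatment emergence once: "A TEAE is defined as an event that first occurred or worsened in severity after the first dose of study treatment in Study JAHN". The severity reference is "The maximum severity for each LLT during the baseline period up to first dose of the study medication in Study JAHN". The same paragraph adds that "The analysis period is defined as the treatment period plus up to 30 days off-drug follow-up time"; in the TEAE sentence this period fixes the last date on which an event may count. No separate start date is given for Period 2.

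Section 6.2.2, under Safety Analyses, says "Safety analyses for Treatment Period 2 will be conducted for AEs only" and then "Baseline for Treatment Period 2 is defined as nonmissing measurements on or prior to the date of first study drug administration in Treatment Period 2". The introduction to Section 6.14 sends the reader there: "The general methods used to summarize safety data, including the definition of baseline value, are described in Section 6.2".

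Table JAHN.6.1 defines the Period 2 safety groups by treatment after Week 52. They include placebo and 1 mg after 2 mg, and placebo and 2 mg after 4 mg. Section 6.2.1 says the final-lock AE tables use these groups. Section 6.14.1 starts Period 2 exposure at the first Period 2 dose.

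**The concern.** Sections 6.14.2 and 6.2.2 set two starting points, about 52 weeks apart, for the same tables. Period 2 safety analysis is confined to AEs, so the Period 2 safety baseline in 6.2.2 has no use other than in AE tables. The SAP does not say which section prevails.

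The choice affects attribution. Suppose a patient develops an event on 2 mg in Period 1, is re-randomised to placebo at Week 52, and still has the event at the same severity. Under 6.14.2 as worded, the event began after the first JAHN dose and exceeds the pre-JAHN severity, so it qualifies as a Period 2 TEAE under placebo. Under 6.2.2 it was already present at baseline and does not qualify. The SAP guards attribution at the other end of follow-up, by censoring at retreatment and by cutting off event data at a dose or treatment change. The start of the TEAE rule has no matching safeguard.

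**Working it through.** The plan states no adverse event rate, so there is no figure of its own to reproduce. The check is a comparison of the two rules on constructed histories, followed by an illustration with assumed rates.

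**Step 1: the two rules applied to constructed histories.** An event counts in Period 2 if its Period 2 severity exceeds the baseline severity. The baseline is the pre-JAHN maximum under 6.14.2. Section 6.2.2 fixes the date of the Period 2 baseline but says neither how far back it reaches nor how severity is summarised over it, so two versions are shown: severity of events ongoing at the first Period 2 dose, and the maximum over all of Period 1.

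| Before JAHN | Period 1 | Period 2 | 6.14.2 as worded | Period 2 baseline, ongoing events | Period 2 baseline, Period 1 maximum |
|---|---|---|---|---|---|
| None | Mild, ongoing at Week 52 | Still mild | TEAE | No | No |
| None | Moderate, ongoing at Week 52 | Eases to mild | TEAE | No | No |
| Mild | Moderate, ongoing at Week 52 | Still moderate | TEAE | No | No |
| None | Mild, ongoing at Week 52 | Worsens to moderate | TEAE | TEAE | TEAE |
| None | None | New mild event | TEAE | TEAE | TEAE |
| None | Mild, resolved | New mild episode | TEAE | TEAE | No |

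The first three rows change status between 6.14.2 and either form of Period 2 baseline. In each, the event arose or worsened in Period 1 and did not worsen in Period 2. The last row shows that the length of the baseline window also matters: a maximum over the whole of Period 1 would hide a genuine new episode.

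**Step 2: illustration of dilution.** All inputs are assumptions. Let p be the true proportion with a TEAE arising or worsening in Period 2, and c the proportion carrying a Period 1 event that qualifies only under 6.14.2. If carrying such an event is independent of having a new one, the reported proportion is 1 − (1 − p)(1 − c).

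- Assumed p: 20% on placebo, 30% on continued dose. True ratio 0.30 / 0.20 = 1.50; true difference 10 points.
- Assumed c: 10% in both arms, because re-randomisation balances Period 1 history in expectation.
- Placebo: 1 − 0.80 × 0.90 = 0.28.
- Continued dose: 1 − 0.70 × 0.90 = 0.37.
- Reported ratio 0.37 / 0.28 = 1.32; reported difference 9 points, which is 10 × (1 − 0.10).

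With c = 0 the ratio stays at 1.50. It also stays at 1.50 with c = 10% if every carrier would have had a new Period 2 TEAE anyway, because nobody is then added to either count. For these assumed rates, the ratio therefore runs from 1.50 (no carry-over, or complete overlap) to 1.32 (10% carry-over, independent).

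**The case against.** The strongest reply is that the SAP already contains a period-specific baseline. Section 6.2.2 sets it, Section 6.14 refers to Section 6.2 for baseline, and 6.14.2 itself speaks of analysis by period. A programmer who followed that chain would avoid the problem. This largely stands: carry-over is what the wording of 6.14.2 permits, not a certain result. It does not remove the conflict. Section 6.14 describes Section 6.2 as general methods, while 6.14.2 gives a specific rule for AEs, and a programmer could as reasonably follow the specific rule. The 30-day analysis period does not help either, since it limits the end of the window and not the start.

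A reader might infer three stronger things that the documents do not support.

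- *That all Period 2 safety comparisons are affected.* Deaths, SAEs and discontinuations due to AEs are reported in their own right and are not defined by treatment emergence. Only the TEAE and severe-TEAE rows depend on this rule.
- *That one re-randomised arm is favoured.* Among patients coming from the same prior dose, randomisation balances Period 1 events in expectation. The effect is higher incidence and weaker contrast, not a shift towards one arm. That protection does not extend to the non-substudy groups or to comparisons across prior doses.
- *That every Period 1 event, including those long resolved, would enter the Period 2 table.* Tables split by period, with groups defined from Week 52, cannot sensibly be read that way. The realistic exposure is to events that persist into Period 2.

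It is also fair to say that Section 6.14 places the fuller safety assessment in pooled analyses under standards not included here, and that Section 6.14.2.1 drops common TEAEs for JAHN alone. The Period 2 TEAE tables are nevertheless planned, including for the final lock, and need one definition.

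**Conclusion.** The point holds as an unreconciled conflict between Sections 6.14.2 and 6.2.2, one side of which gives the wrong attribution if followed literally. Under 6.14.2 as worded, an event that began in Period 1 and persists at the same severity counts as a TEAE under the Period 2 treatment. That inflates Period 2 TEAE and severe-TEAE incidence and tends to dilute contrasts in those rows.

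The size cannot be derived from the documents. The fall in ratio from 1.50 to 1.32 rests on assumed rates, an assumed 10% carry-over equal in both arms, and independence; greater overlap between carried and new events shrinks it, to nothing at the extreme. The text does not support saying that the tables will be wrong, because a programmer who applied 6.2.2 would not produce the carry-over.

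**What to change.** In Section 6.14.2, state that for Period 2 tables a TEAE is an event that first occurred or worsened after the first Period 2 dose, and cross-refer to 6.2.2 so that the two sections agree.

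Then define the Period 2 baseline window for LLT severity, which 6.2.2 leaves open. One workable choice is the severity of events ongoing at the first Period 2 dose, rather than the maximum over all of Period 1. A new Period 2 episode of a resolved Period 1 event then still counts. The text should also say how an event ongoing at Week 52 is handled.

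The cost is one or two sentences and a second treatment-emergent flag in the AE dataset; no new data are needed. Where the tables would otherwise have followed 6.14.2 as worded, Period 2 TEAE counts will be smaller.
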